3.1.7. Zubrod Performance Status 0-2

- 3.1.8. Age  $\geq$  18
- 3.1.9. Baseline serum PSA value performed with an FDA-approved assay (e.g., Abbott, Hybritech) within 60 days prior to registration
- 3.1.10. Baseline serum testosterone obtained within 60 days prior to registration
- 3.1.11. Study entry PSA and serum testosterone must not be obtained during the following time frames: (1) 10-day period following prostate biopsy; (2) following initiation of oral androgen manipulation; (3) within 30 days after discontinuation of finasteride or dutasteride
- 3.1.12. CBC/differential obtained within 60 days prior to registration with adequate bone marrow function defined as follows:
- Absolute neutrophil count (ANC)  $\geq$  1,800 cells/mm^3
  - Platelets  $\geq$  100,000 cells/mm^3
  - Hemoglobin  $\geq$  8.0 g/dl (Note: The use of transfusion or other intervention to achieve Hgb  $\geq$  8.0 g/dl is acceptable.)
- 3.1.13. Patient must be able to provide study-specific informed consent prior to study entry.
- 3.1.14. Liver function parameters as follows:
- Total Bilirubin  $\leq$  2 x institutional upper limit of normal
  - AST (SGOT) or ALT (SGPT)  $\leq$  2 x institutional upper limit normal

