## **4. TREATMENT PLAN**

### **4.1. Dual Oral Androgen Manipulation**

Treatment will be administered on an outpatient basis. Reported adverse events and potential risks are described in Section 6.

After study enrollment, patients will initiate dual oral androgen manipulation therapy consisting of an androgen receptor blocker and a 5AR inhibitor according to the following dose and route schedules:

- Bicalutamide 50 mg PO daily
- Dutasteride 0.5 mg PO daily (recommended) or Finasteride 5 mg PO daily

During week 6-8 of oral androgen manipulation therapy, patients will undergo CT simulation for radiation planning. After 8 weeks of hormonal therapy, patients will begin dose escalated radiation with concurrent androgen manipulation for approximately 7-8 weeks, Monday through Friday. Details regarding planning and administration of RT are described in Section 5.

Following completion of radiation, having completed 4 total months of dual androgen manipulation, patients will discontinue Bicalutamide. All patients will continue taking the 5AR inhibitor as monotherapy for 2 years after completion of radiation for a total of 2 years, 4 months of treatment.

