### 7. STUDY CALENDAR

Baseline evaluations (including performance status, history and physical, scans) are to be conducted within 60 days prior to the start of protocol therapy.

	Baseline	Month 2 (pre-RT)	Month 3-4 (during RT)	Month 6 (2 mos post- RT)	Month 10 (6 mos post-RT)	Month 16 (12 mos post-RT)	Month 22 (18 mos post-RT)	Month 28 (24 mos p RT)
Inclusion/ exclusion	X							
Informed Consent	X							
Path confirms cancer	X							
History and Physical	X	X	X**	X	X	X	X	X
Vital Signs, weight	X		X**	X	X	X	X	X
Zubrod Performance status and Charlson index	X							
Document Current Medicines	X	X	X**	X	X	X	X	X
CT Ab/Pelvis OR MRI*	X							
Bone Scan *	X							
Tumor tissue collection	X	X						
CBC with differential and CMP	X	X	X#	X		X		X
Toxicity Assessment			X**	X	X	X	X	X
Patient Outcome Questionnaire	X	X		X	X	X≠	X≠	X≠
PSA	X	X		X	X	X	X	X

Total, serum Testosterone	X	X				X		X
---------------------------	---	---	--	--	--	---	--	---

^ This evaluation will occur at the planning stage before radiation therapy has begun (e.g. fiducial marker placement or simulation)

\* See Section 3 for requirements/exceptions \*\* Weekly during radiation treatment

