# These labs will be drawn in the last week of radiation therapy

≠ Optional

Note that the protocol allows for 1 month of flexibility to meet any follow-up appointment time (e.g. the month 6 visit may occur at month 5 or month 7.)

Beyond month 10, follow-up is recommended but not required. All data collected between month 10 and month 28 will be registered under this study so that longer term quality of life data (beyond the primary endpoint of 6 months) may be analyzed.

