### **9.3. Analysis of Secondary Endpoints**

As secondary endpoints, the study will investigate oncologic outcomes of the prescribed protocol therapy including biochemical progression-free survival, distant metastasis-free survival, cause specific survival, and overall survival. Kaplan-Meier curves will be generated for each endpoint. Findings will be compared to a synchronous cohort of controls.

Biochemical progression free survival will be defined to be the time from the start of therapy with oral androgen manipulation until PSA failure occurs as defined by the Phoenix definition of a rise to 2 ng/ml above the nadir PSA value. The relative hazard for a PSA failure in patients on protocol therapy compared to those in the control cohort will be calculated using the proportional hazards regression model of Cox, but formal statistical conclusions will not be drawn from this analysis.

Hematologic effects of dual oral androgen manipulation will be assessed using hemoglobin levels from scheduled CBC's. Changes in mean hemoglobin between baseline and various time points throughout treatment will be assessed. Univariate analysis of mean scores will be performed using a two sample t-test.

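### Section 9.3 names a two-sample t-test for hemoglobin change from baseline in the same men; it ignores the pairing and makes the standard error too wide

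*Combined protocol and SAP*

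**What the plan says.** The last paragraph of section 9.3 sets the target: "Hematologic effects of dual oral androgen manipulation will be assessed using hemoglobin levels from scheduled CBC's". The contrast is given as "Changes in mean hemoglobin between baseline and various time points throughout treatment will be assessed", and the method as "Univariate analysis of mean scores will be performed using a two sample t-test". The paragraph names no comparator, paired analysis, confidence interval or main time point.

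The study calendar (section 7) has a row for "CBC with differential and CMP", marked at baseline, month 2, month 3-4, and months 6, 16 and 28. A note fixes the month 3-4 draw: "These labs will be drawn in the last week of radiation therapy". The month 2 column is headed as pre-RT, and another note, whose anchor is not visible in the table as extracted, reads "This evaluation will occur at the planning stage before radiation therapy has begun". Section 4.1 starts radiation after 8 weeks of oral therapy and ends the dual phase with it: "Following completion of radiation, having completed 4 total months of dual androgen manipulation, patients will discontinue Bicalutamide". The 5AR inhibitor then continues alone for two years.

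**The concern.** A change from baseline is measured within a man. A two-sample t-test treats the baseline and follow-up values as coming from different people, so it leaves the correlation between a man's two values out of the standard error. When that correlation is positive, the interval is too wide and the test has less power than the data allow.

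The analysis looks for a possible harm. Section 2.2 lists anemia among the toxicities of GnRH agonists, so whether the oral regimen lowers hemoglobin is a natural question for the randomized study that this trial is meant to inform. With the named test, a real fall is more likely to be reported as no detectable change.

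A second, smaller matter is labelling. Section 9.3 attributes the result to dual therapy, but the scheduled draws fall under three different exposures and the section does not say which draws carry the dual-therapy label.

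**Working it through.** **The plan's own figure.** No figure is given for hemoglobin. The only sizing figure is in section 9.2: a 95% interval of plus or minus 15% for a success rate of 0.6 with n = 40. It reproduces: 1.96 × sqrt(0.6 × 0.4 / 40) = 0.152. It concerns a proportion and does not bear on this point.

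**Inputs.** n = 40 experimental subjects (section 9.2). Hemoglobin SD, within-man correlation r, size of fall and alpha are not stated. Assumed: equal SD s at both times, r from 0.3 to 0.8, a fall of 0.3 or 0.5 SD, two-sided alpha 0.05, and all 40 pairs complete.

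**Standard errors.**
- Two-sample: s × sqrt(2/n).
- Paired: s × sqrt(2(1 - r)/n).
- Ratio: 1/sqrt(1 - r), which depends on neither s nor n.

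For illustration, with an assumed s of 1.3 g/dl, the two-sample value is 1.3 × sqrt(2/40) = 0.29 g/dl. The paired value is 1.3 × sqrt(1/40) = 0.21 at r = 0.5 and 1.3 × sqrt(0.4/40) = 0.13 at r = 0.8.

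**Size and power.** True size is approximately 2 × (1 - Φ(1.96 × ratio)). Power comes from 40,000 simulated trials of 40 pairs at each setting.

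| r | SE ratio | True size of nominal 5% two-sample test | Power, fall of 0.3 SD: two-sample / paired | Power, fall of 0.5 SD: two-sample / paired |
|---|---|---|---|---|
| 0.3 | 1.20 | 1.9% | 23% / 35% | 62% / 74% |
| 0.5 | 1.41 | 0.6% | 19% / 45% | 64% / 87% |
| 0.7 | 1.83 | about 0.04% | 14% / 67% | 67% / 98% |
| 0.8 | 2.24 | below 0.01% | 10% / 83% | 70% / >99% |

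The paired test is better in every row. The size of the loss varies widely: 12 percentage points at r = 0.3 for either fall, and 73 points at r = 0.8 for a fall of 0.3 SD.

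**Exposure at each draw** (section 7 set against section 4.1).

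| Draw | Exposure |
|---|---|
| Month 2 | Dual therapy, before RT |
| Last week of RT | Dual therapy plus RT |
| Months 6, 16, 28 | 5AR inhibitor alone, after RT |

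Two of the five post-baseline draws are on dual therapy, and one of those is free of radiation. The calendar notes make follow-up after month 10 optional, so three post-baseline draws are required (month 2, last week of RT, month 6). Two of those three are on dual therapy.

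**The case against.** The strongest objection is that a comparison with controls was meant. The test sentence nearly repeats one in section 9.1, where it does compare cohorts. The first paragraph of 9.3 says findings will be compared with synchronous controls, and section 4.3 allows control data to be taken from the medical record. If changes were compared between cohorts, a two-sample test would be valid and the figures above would not apply. This reading is possible, but the hemoglobin paragraph does not state it. That paragraph contrasts baseline with later times and names no control group. The comparison sentence in 9.3 follows the oncologic endpoints, the cohort comparison in 9.1 covers quality of life and toxicity scores, and section 4.3 leaves control laboratory tests outside the protocol schedule.

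Four stronger readings are tempting, and the documents do not support them:
- **That all draws are pooled into one dual-therapy effect.** Section 9.3 leaves the time points unnamed. It says neither that every draw is used nor that they are combined, and reporting by visit would already separate the phases.
- **That only month 2 can answer the question.** The regimen under study is oral therapy given with radiation, and month 2 covers about half of the four-month dual phase. Making it the sole main estimate is partly a preference.
- **That the results would be biased toward the oral regimen.** A missed fall would favour it, but a fall due to radiation would be charged against it. No net direction is shown.
- **That transfused baselines distort the result.** Section 3.1.12 does accept "The use of transfusion or other intervention to achieve Hgb" of at least 8.0 g/dl, but nothing indicates how often this would occur.

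It is also fair to say that the error is conservative, that hemoglobin appears in no objective, success criterion or stopping rule, and that the test can be corrected at analysis from the same data. All of this stands and limits the weight of the point.

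**Conclusion.** As written, the test does not match the contrast. The overstatement of the standard error, 1.2 to 2.2 times, rests only on the assumed correlation range and equal variances. The power loss rests in addition on assumed effect sizes and complete pairs, so no single power figure should be quoted as the plan's. Type I error is not inflated. The consequence is a lower chance of detecting a real fall in hemoglobin, together with an exposure label that fits only the month 2 and end-of-RT draws. This is a minor correction to a secondary analysis in a feasibility study; the HRQOL primary endpoint is untouched.

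**What to change.** In section 9.3:
- Replace the two-sample t-test with the paired within-man change from baseline at each scheduled CBC, with a 95% CI and a paired t-test, or with a mixed model for repeated measures.
- Report each draw under its exposure, as in the second table above, and do not pool them. Describe only the first two draws as on dual therapy, and only month 2 as free of radiation.
- State whether controls are compared. If they are, keep the two-sample test for differences in change between cohorts, limited to controls whose CBCs exist in the record.

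The cost is a few sentences. No new samples or visits are needed, because every CBC is already on the calendar.

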## **10. CONFIDENTIALITY**

Study records that identify patients will be kept confidential. Study records will contain patients' name, address, and medical history number, and will be available to the study doctor, research nurse, and data coordinator. Data collected in this study will be maintained on a password protected computer that only the principal investigator, co-investigators, research nurse, and data coordinator will be able to access. Study records will be secured in locked offices in the Department of Radiation and Cellular Oncology. Neither patient names nor other personally identifying information will be used in any publication resulting from the research study.

**APPENDIX A:**

**DEPARTMENT OF RADIATION AND CELLULAR ONCOLOGY**

**DIVISION OF THE BIOLOGICAL SCIENCES AND  
THE PRITZKER SCHOOL OF MEDICINE**

This questionnaire is designed to measure Quality of Life issues in patients with Prostate Cancer. To help us get the most accurate measurement, it is important that you answer all questions honestly and completely. **Please note that there are 2 sides on each page.**

Remember, as with all medical records, information contained with this survey will remain strictly confidential.

Name : \_\_\_\_\_ Today's Date: Month \_\_\_\_\_ Day \_\_\_\_ Year \_\_\_\_\_

**The following questions are about your general health.**

List any health problems, including diagnosis of any other cancers, that have required new therapy (such as medicines or procedures) or hospitalization **since your last visit**:

List the date of any recent colonoscopy (examination of the colon using a camera): \_\_\_\_\_

List the date of any recent cystoscopy (examination of the bladder using a camera): \_\_\_\_\_

Include the names, addresses, and phone/fax numbers of any physicians who are actively involved with your medical care. We will send documentation of your clinic visit to any physicians listed here.

Physician use only	Grade	Comment
GI		
GU		
Sexual		
Other		

**The following questions are about your urinary function.**

1. Over the **past 4 weeks**, how often have you leaked urine?

- More than once a day..... 1
  - About once a day..... 2
  - More than once a week..... 3
  - About once a week..... 4
  - Rarely or never ..... 5
- (Circle one number)

2. Which of the following best describes your urinary control **during the last 4 weeks**?

- No urinary control whatsoever..... 1
  - Frequent dribbling..... 2
  - Occasional dribbling..... 3
  - Total control..... 4
- (Circle one number)

3. How many pads or adult diapers per day did you usually use to control leakage **during the last 4 weeks**?

- None..... 0
  - 1 pad per day..... 1
  - 2 pads per day..... 2
  - 3 or more pads per day..... 3
- (Circle one number)

4. How big a problem, if any, has each of the following been for you **during the last 4 weeks**?

(Circle one number on each line)

	No Problem	Very Small Problem	Small Problem	Moderate Problem	Big Problem
a. Dripping or leaking urine .....	0	1	2	3	4
b. Pain or burning on urination ...	0	1	2	3	4
c. Bleeding with urination .....	0	1	2	3	4
d. Weak urine stream or incomplete emptying .....	0	1	2	3	4
e. Waking up to urinate .....	0	1	2	3	4
f. Need to urinate frequently during the day .....	0	1	2	3	4

5. Overall, how big a problem has your urinary function been for you **during the last 4 weeks**?

- No problem..... 1
  - Very small problem..... 2
  - Small problem..... 3
  - Moderate problem..... 4
  - Big problem..... 5
- (Circle one number)

6. International Prostate Symptom Score (IPSS). The following questions are about symptoms **during the last 4 weeks**.

	Not at all	Less than 1 time in 5	Less than half the time	About half the time	More than half the time	Almost always	Your score
a. Incomplete emptying How often have you had a sensation of not emptying your bladder completely after you finish urinating?	0	1	2	3	4	5	
b. Frequency How often have you had to urinate again less than two hours after you finish urinating?	0	1	2	3	4	5	
c. Intermittency How often have you found you stopped and started again several times when you urinated?	0	1	2	3	4	5	
d. Urgency How often have you found it difficult to postpone urination?	0	1	2	3	4	5	
e. Weak stream How often have you had a weak urinary stream?	0	1	2	3	4	5	
f. Straining How often have you had to push or strain to begin urinating?	0	1	2	3	4	5	
	None	1 time	2 times	3 times	4 times	≥5 times	
g. Nocturia How many times did you most typically get up to urinate each night from the time you went to bed at night to the time you got up the next morning?	0	1	2	3	4	5	

TOTAL IPSS SCORE:

Quality of life: If you were to spend the rest of your life with your urinary condition just the way it is now, how would you feel about that?	Delighted 0	Pleased 1	Mostly satisfied 2	Mixed 3	Mostly dissatisfied 4	Unhappy 5	Terrible 6
--	----------------	--------------	-----------------------	------------	--------------------------	--------------	---------------

**The following questions are about your bowel function.**

7. How often have you had rectal urgency (felt like you had to pass stool, but did not) **during the last 4 weeks?**  
 More than once a day ..... 1  
 About once a day ..... 2  
 More than once a week ..... 3 (Circle one number)  
 About once a week ..... 4  
 Rarely or never ..... 5

8. How often have you had stools that were loose or liquid (no form, watery, mushy) **during the last 4 weeks?**  
 Never..... 1  
 Rarely..... 2  
 About half the time..... 3 (Circle one number)  
 Usually..... 4  
 Always..... 5

9. How often have you had bloody stools **during the last 4 weeks?**  
 Never..... 1  
 Rarely..... 2  
 About half the time..... 3 (Circle one number)  
 Usually..... 4  
 Always..... 5

10. How big a problem, if any, has each of the following been for you? (Circle one number on each line)

	No Problem	Very Small Problem	Small Problem	Moderate Problem	Big Problem
a. Urgency to have a bowel movement ..... 0		1	2	3	4
b. Increased frequency of bowel movements ..... 0		1	2	3	4
c. Watery bowel movements. 0		1	2	3	4
d. Losing control of your stools ..... 0		1	2	3	4
d. Bloody stools ..... 0		1	2	3	4
e. Abdominal/Pelvic Rectal pain ..... 0		1	2	3	4

11. Overall, how big a problem have your bowel habits been for you **during the last 4 weeks?**  
 No Problem..... 1  
 Very Small Problem..... 2  
 Small Problem..... 3 (Circle one number)  
 Moderate Problem..... 4  
 Big Problem..... 5

**The following questions are about your sexual function.**

12. How would you rate each of the following **during the last 4 weeks?** (Circle one number on each line)

	Very Poor/ None	Poor	Fair	Good	Very Good
a. Your level of sexual desire?	1	2	3	4	5
b. Your ability to have an erection?	1	2	3	4	5
c. Your ability to reach orgasm (climax)?	1	2	3	4	5

13. How would you describe the usual **QUALITY** of your erections **WITHOUT** assistance of medicines or devices **during the last 4 weeks?**

- None at all..... 1
- Not firm enough for any sexual activity..... 2
- Firm enough for masturbation and foreplay only..... 3 (Circle one number)
- Firm enough for intercourse..... 4

14. How would you describe the usual **QUALITY** of your erections (**WITH** assistance of medicines or devices if needed) **during the last 4 weeks?**

- None at all..... 1
- Not firm enough for any sexual activity..... 2
- Firm enough for masturbation and foreplay only..... 3 (Circle one number)
- Firm enough for intercourse..... 4

15. Regarding the use of any medications or devices to aid or improve erections:

	Have NOT tried it	Tried it, but was NOT HELPFUL	It HELPED, but I am NOT using it NOW	It HELPED, and I use it sometimes	It HELPED, and I use it always
a. Viagra or other pill (name if not viagra): _____ Dose used: _____	1	2	3	4	5
b. Vacuum erection device (such as erect-aid)	1	2	3	4	5
c. Muse (intra-urethral alprostadil suppository)	1	2	3	4	5
d. Penile injection therapy (such as caverject)	1	2	3	4	5
e. Other (if not listed): _____	1	2	3	4	5

16. How would you describe the **FREQUENCY** of your erections **during the last 4 weeks?**

- I NEVER had an erection when I wanted one..... 1
- I had an erection LESS THAN HALF the time I wanted one..... 2
- I had an erection ABOUT HALF the time I wanted one..... 3 (Circle one number)
- I had an erection MORE THAN HALF the time I wanted one..... 4
- I had an erection WHENEVER I wanted one..... 5

17. **During the last 4 weeks**, how often did you have sexual intercourse?

- Not at all ..... 1
- Less than once a week ..... 2
- About once a week ..... 3 (Circle one number)
- Several times a week ..... 4
- Daily ..... 5

18. Overall, how would you rate your ability to function sexually **during the last 4 weeks?**

- Very poor..... 1
- Poor..... 2
- Fair..... 3 (Circle one number)
- Good..... 4
- Very good..... 5

19. Overall, how big a problem has your sexual function or lack of sexual function been for you **during the last 4 weeks?**

- No Problem..... 1
- Very small problem..... 2
- Small problem..... 3 (Circle one number)
- Moderate problem..... 4
- Big problem..... 5

20. Sexual Health Inventory for Men (SHIM). Answer the following questions, including the use of medications or devices if you use them.

a. How do you rate your confidence that you could get and keep an erection?

- |          |     |          |      |           |
|----------|-----|----------|------|-----------|
| Very low | Low | Moderate | High | Very high |
| 1        | 2   | 3        | 4    | 5         |

b. When you had erections with sexual stimulation, how often were your erections hard enough for penetration (entering your partner)?

- |                    |                       |  |                           |   |                         |
|--------------------|-----------------------|--|---------------------------|---|-------------------------|
| No sexual activity | Almost never or never | A few times (much less than half the time) | Sometimes (half the time) | Most times (much more than half the time) | Almost always or always |
| 0                  | 1                     | 2  | 3                         | 4   | 5                       |

c. During sexual intercourse, how often were you able to maintain your erection after you had penetrated (entered) your partner?

- |                             |                       |  |                           |   |                         |
|-----------------------------|-----------------------|--|---------------------------|---|-------------------------|
| Did not attempt intercourse | Almost never or never | A few times (much less than half the time) | Sometimes (half the time) | Most times (much more than half the time) | Almost always or always |
| 0                           | 1                     | 2  | 3                         | 4   | 5                       |

d. During sexual intercourse, how difficult was it to maintain your erection to completion of intercourse?

- |                             |                     |                |           |                    |               |
|-----------------------------|---------------------|----------------|-----------|--------------------|---------------|
| Did not attempt intercourse | Extremely difficult | Very difficult | Difficult | Slightly difficult | Not difficult |
| 0                           | 1                   | 2              | 3         | 4                  | 5             |

e. When you attempted sexual intercourse, how often was it satisfactory for you?

- |                             |                       |  |                           |   |                         |
|-----------------------------|-----------------------|--|---------------------------|---|-------------------------|
| Did not attempt intercourse | Almost never or never | A few times (much less than half the time) | Sometimes (half the time) | Most times (much more than half the time) | Almost always or always |
| 0                           | 1                     | 2  | 3                         | 4   | 5                       |

TOTAL SHIM SCORE:

